The center is the earliest unit in our province to carry out HSCT treatment of hematological diseases, and the technical level of HSCT is in the leading position in the province, and it has a solid clinical application conditions and foundation. We are willing to accept and adopt the new concept and treatment of hypertransplantation in [name] team, and carry out clinical research on the treatment of thalassemia major under the guidance and help of [name], verify its "safety and efficacy", cure patients and promote the continuous development of science, and create a safe and effective new treatment model for the treatment of thalassemia major without pretreatment, reproductive damage, and post-transplant complications.

2. Research objectives

It is planned to recruit 3-5 patients with thalassemia major without HSCT indication and unable to undergo thalassemia gene therapy from June 01, 2024 to June 2025, and use the super transplantation treatment plan of [name] team to observe the cell reinfusion response, hematopoietic remodeling, hemoglobin level and blood transfusion, thalassemia clonal clearance, immune reconstitution, endocrine function recovery, gastrointestinal function recovery, infection and other complication rates. To verify the safety and efficacy of super transplantation in the treatment of thalassemia major.

3. Research design and methodology

(1) Research Design:

1. This study is a single-center, single-arm, prospective clinical study. There is no control and no blinding.

2. Subject recruitment and management

1) Patient recruitment: The center publishes recruitment information to screen patients who meet the inclusion criteria;

2) Patients were enrolled after signing the informed consent form;

3) Check the inclusion criteria: Subjects are included in strict accordance with the inclusion criteria, and if there is any situation described in the exclusion criteria, the subjects will be excluded in a timely manner, and a special person will be responsible for checking and recording relevant information.

4) Collect medical history and complete the personal information and medical history part of the study record form.

3. Lifestyle requirements

Patients should be on a hyperbaric sterile diet from the beginning of the super graft

process, and dietary hygiene should be observed. Different stages of the period have different dietary requirements, and subjects and their families should follow the arrangements of medical staff.

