4. Withdrawal criteria for subjects

The study physician and the sponsor may also request to stop or withdraw from this study for the following reasons:

- (1). Serious safety problems occur during the test;
- (2). There are serious complications that the investigator deems necessary to terminate the trial treatment;
- (3). From the perspective of the patient's interests, the best choice for the investigator is to terminate the trial treatment;
- (4). The subject withdraws the informed consent or actively asks to withdraw;
- (5) The subject has progressed and is no longer suitable to participate in this study;
- (6). The subject had poor compliance during the trial, refused to cooperate with the treatment and follow-up, and could not continue the study.

Subjects will still be provided with appropriate treatment options after withdrawing from the pilot study, and subjects can withdraw from the study without discrimination or retaliation after notifying the investigator at any stage of the trial, and any medical treatment and rights will not be affected as a result. After withdrawing from the study, the subjects will still be informed in detail of the appropriate medical plan for continuation, and the subjects will still be regularly followed up and guided to guide the follow-up treatment of the patients.

5. Description of the study intervention

This study is a prospective, single-center, single-arm clinical study, and it is planned to include 3-5 patients with thalassemia major who have no HSCT indication and cannot receive thalassemia gene therapy. The diagnosis of thalassemia major was determined by the thalassemia genotype and the clinical manifestations of the patients, and the patients who met the inclusion criteria and did not meet the exclusion criteria were screened and enrolled and received super transplantation therapy. Hypertransplantation is an innovative treatment plan of [name] team, which uses hematopoietic stem cell transplantation from healthy donors with the same haplotype as the patient, and observes the patient's cell reinfusion response, hematopoietic reconstitution, hemoglobin level and blood transfusion, thalassemia clonal clearance, immune

reconstitution, endocrine function recovery, gastrointestinal function recovery, as well as the incidence of graft-versus-host disease, infection and other complications after transplantation.

The duration of follow-up was 24 months. Follow-up visits include:

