1) G-CSF mobilization and donor collection: the same as the conventional peripheral blood mononuclear cell (PBMC) protocol.

2) Transplantation plan and treatment principles:

(1) Pretreatment: None.

(2) GVHD prophylaxis: 1/2 dose of conventional transplant GVHD prophylaxis, and the use time is half a year, see separate article for details.

(3) Donor cell infusion, etc., are detailed in a separate article.

(4) Prevention and treatment of complications: fungal, pulmonary prevention programs and antiviral treatment.

3. Follow-up period: All subjects started on the first day after transplantation and were followed up to 24 months after transplantation. The patient's cell reinfusion reaction, hematopoietic reconstitution, hemoglobin level and blood transfusion, thalassemia clonal clearance, immune reconstitution, endocrine function recovery, gastrointestinal function recovery, infection and other complications were recorded.

8. Evaluation

1) Efficacy evaluation:

Main indicator: Donor cell engraftment rate, time: 3 months after transplantation.

Secondary indicators: thalassemia gene carriage, growth and development assessment, time: 1 year.

2) Safety evaluation

Main indicator: transplant-related death, time: 3 months after transplantation.

Secondary indicators: GVHD, infectious complications, time: 1 year.

Any adverse events that occur are recorded during the study period and treated in a timely manner, and the patient's vital signs, physical examination, laboratory tests, etc. are recorded in detail. In this trial, corresponding management and treatment measures have been formulated for potential major risk events such as allergic reactions and infections.

- 1) Physical examination: examination of all systems of the whole body;
- 2) Vital signs: body temperature, respiration, heart rate, blood pressure;
- 3) Laboratory tests: blood routine, urine routine, blood biochemistry, electrolytes, coagulation function;
- 4) 12-lead ECG;
- 5) Detection of infectious markers;
- 6) Adverse events and serious adverse events. The severity of adverse events was based on the CTCAE version 5.0 classification criteria.

9. Statistical analysis and statistical methods

(1) General method

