In this study, descriptive statistics and multivariate regression analysis were used, absolute numbers were used for categorical data, and median data were used for continuous data, and chi-square test and nonparametric test were mainly used, $p < 0.05$ was statistically significant.

and (2) analysis of primary and secondary study endpoints

(3) Safety analysis

AEs were coded and calculated, which could be expressed in terms of severity, frequency, and association with the intervention. Adverse events leading to discontinuation of study intervention and serious AEs resulting from treatment should be listed individually.

(4) Baseline descriptive analysis

Descriptive statistics were used to compare demographic characteristics and laboratory indicators at baseline between groups.

(5) Subgroup analysis

The study endpoints could be analyzed according to the transplantation conditioning regimen, pre-transplantation remission status, age, neutrophil and platelet engraftment

time, etc., and the association between the primary and secondary study endpoints and different factors could be evaluated by COX regression.

10. Quality control and quality assurance

In order to ensure that the trial can be carried out in strict accordance with the clinical research protocol, in the process of clinical trial, the clinical investigator, the sponsor and the clinical supervisor should operate in accordance with the requirements of the clinical trial quality management practice, and must ensure that the test procedures are standardized, the experimental data are accurate, the experimental data are traceable, and the research conclusions are reliable.

IV. Inclusion and exclusion guidelines

(1) Patient enrollment criteria:

Patient inclusion criteria (the following 4 criteria must be fully met):

- 1) Confirmed diagnosis of thalassemia major, regardless of α and β type;
- 2) Age between 7-12 years old, male or female; Weight < 40kg
- 3) Patients with or without HLA-matched or haploidentical donors, but unconditionally transplanted or refused to undergo blood stem cell transplantation; Patients who are unconditional or refuse to undergo thalassemia gene therapy;
- 4) There are HLA fully compatible or incompatible donors, and the physical examination meets the donor conditions;
- 5) The patient and his or her family agree to receive ultra-transplantation therapy and sign a written informed consent form before the transplantation trial.

(2) Patient exclusion criteria:

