(1) Medical treatment and protection of subjects after the research process

After the research process, the subjects will still be informed in detail of the continued medical plan, and the subjects will still be regularly followed up and guided to treat, and the follow-up treatment of the patients will be guided in detail.

6. Adverse events and serious adverse events

It is the responsibility of the investigator to ensure that all AEs reported by the subject after the investigator's observation have been reported in the eCRF during the post-study safety follow-up period since the subject started study treatment, and at any time during the safety follow-up after the end of study treatment, the investigator should report any AEs that the investigator believes may be relevant to study dosing, and during the safety follow-up period, the investigator should report all SAEs.

Any serious adverse events that occur in the trial, regardless of whether they are related to the trial intervention, should be promptly rescued by the investigator, and the Serious

Adverse Event (SAE) Report Form provided by the sponsor should be filled in and dated within 24 hours after being informed, and reported to the sponsor immediately. SAEs should detail a description of symptoms, severity, time of onset, time of treatment, measures taken, timing and manner of follow-up, and prognosis. Serious adverse event reports and follow-up reports should indicate the identification code of the subject in the clinical trial, rather than the identity information such as the subject's real name, ID number and address.

7. Benefits and risks

7.1 Benefits:

- 1) Obtain a chance of thalassemia major cure;
- 2) Free of charge: donor stem cell mobilization and collection, stem cell infusion pretreatment, lymphocyte subsets and cytokine detection 12 times, thalassemia gene detection 13 times, donor DNA mosaic rate monitoring 12 times. The total monitoring cost is about 40,000 yuan.
- 4) Insurance 200 yuan/person, insurance amount 200,000.

7.2 Risks:

During the treatment, there is a risk of adverse reactions such as donor implantation failure, cytokine release syndrome, graft-versus-host disease, drug side effects, infection, etc., which are associated with transplant therapy and cannot be completely avoided.

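### The only mortality indicator is transplant-related death at 3 months, so a death judged unrelated can be missing from both the main safety result and the individual listing

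*Protocol*

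**What the plan says.** All references are to the protocol.

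- **Section 8, Safety evaluation.** The endpoint is "Main indicator: transplant-related death, time: 3 months after transplantation". The secondary safety indicators are graft-versus-host disease and infections, at one year. Neither overall survival nor death from any cause appears.
- **Section 3, Research design, item 1.** The study has one centre and one arm: "There is no control and no blinding".
- **Section 2, Research objectives.** "It is planned to recruit 3-5 patients with thalassemia major". The description of the intervention repeats the number.
- **Section 9, item (3), Safety analysis.** Besides events leading to discontinuation of the intervention, "serious AEs resulting from treatment should be listed individually". The listing is thus limited by relatedness.
- **Subject protection measures, item 6.** Reporting to the sponsor is wider. It covers "Any serious adverse events that occur in the trial, regardless of whether they are related to the trial intervention".
- **Follow-up.** Patients are followed to 24 months after transplantation.

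**The concern.** Transplant-related death is a cause-specific count: a death enters it only after someone decides that the transplant caused it. There is no comparison group against which a background death rate could be seen, so that decision carries much of the weight of the main safety result.

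The decision will not always be obvious. The background section describes heart damage from long-term anaemia and iron deposition in the liver in these patients. A cardiac death in the first weeks could reasonably be assigned to the underlying disease.

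At stake is whether a report of no transplant-related deaths would tell the reader that nobody died. Under the indicators as written it would not. The individual listing, where a reader would look next, is filtered by the same kind of judgement. A death in month 4 or later is outside the main indicator whatever its cause.

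**Working it through.** **Step 1: where would a death appear?** Take four hypothetical deaths and apply the text of section 8 (indicator), section 9 item (3) (individual listing) and subject protection item 6 (report to the sponsor).

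| Death | Main safety indicator | Individual listing | Report to sponsor |
|---|---|---|---|
| By month 3, judged related | Counted | Listed | Yes |
| By month 3, judged unrelated | Not counted | Only if also classed as leading to discontinuation | Yes |
| After month 3, judged related | Not counted | Listed | Yes |
| After month 3, judged unrelated | Not counted | Only if also classed as leading to discontinuation | Yes |

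The second and fourth rows are the gap. These deaths are on record with the sponsor, but the planned outputs need not show them. The one-year secondary indicators do not close the gap. They would register an infection or graft-versus-host disease as an event, not the fact that a patient died, and they would not register a cardiac death at all.

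**Step 2: what does the choice of indicator change?** Counting all deaths to month 3 moves the second row into the main result. Reporting all deaths to month 24 brings in the third and fourth rows. Neither count needs a causality judgement.

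**Step 3: size of one death.** The protocol states no expected death rate, safety threshold or sample-size calculation, so there is no figure of its own to reproduce. The input is n = 3 to 5. One death changes the proportion by 1/n:

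- n = 3: 1/3 = 33.3 percentage points
- n = 4: 1/4 = 25.0
- n = 5: 1/5 = 20.0

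Exact (Clopper-Pearson) 95% limits. With no counted death, the upper limit is 1 − 0.025^(1/n). With one counted death, the lower limit is 1 − 0.975^(1/n) and the upper limit is the 97.5% quantile of a Beta(2, n − 1) distribution.

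| n | 0 deaths counted | 1 death counted |
|---|---|---|
| 3 | 0% (0 to 70.8%) | 33.3% (0.8 to 90.6%) |
| 4 | 0% (0 to 60.2%) | 25.0% (0.6 to 80.6%) |
| 5 | 0% (0 to 52.2%) | 20.0% (0.5 to 71.6%) |

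The step is the same whether deaths are counted by cause or all together. It shows how small the study is. The choice of indicator decides only whether the step also depends on a relatedness judgement.

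**The case against.** The strongest reply is that nothing is concealed. Serious adverse events go to the sponsor "regardless of whether they are related to the trial intervention", and section 9 lets adverse events be summarised by severity, frequency and association. This is right as far as collection goes, and it is why the change is cheap. It does not settle the outputs: the summary wording is permissive, and the one firm instruction on individual listing is limited to treatment-related serious events and discontinuations. One can argue that a death during the half-year of prophylaxis is also a discontinuation, but the protocol does not say so.

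A second reply is that transplant-related death is a recognised endpoint. That stands, and it is a reason to keep it, though not as the sole mortality measure.

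Four stronger readings are tempting and should not be adopted.

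- *That the protocol has unblinded investigators attribute the deaths.* It does not say who attributes them. The nearest text concerns adverse events in general: "the investigator should report any AEs that the investigator believes may be relevant to study dosing". A definition and an adjudication process may stand in an analysis plan or charter that is not shown, so their absence here is not counted as a fault. Lack of blinding also adds little, because a single-arm study has no allocation to conceal.
- *That deaths from infection or graft failure could readily be called unrelated.* The risk statement (item 7.2) names both among the risks tied to the transplant. It is not an attribution rule, but it points towards counting them. Iron-related heart disease is the better example.
- *That the 20 to 33 points measure attribution bias.* They are 1/n and presuppose a death.
- *That counting all deaths would allow comparison with the survival rates in the background section.* Those are 5-year figures, and no comparison with them is planned. Death to 3 or 24 months still has a different horizon.

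**Conclusion.** The point holds in a limited form. The plan names one mortality indicator. It is cause-specific and stops at 3 months, and the individual listing is also restricted by relatedness. A death judged unrelated could be missing from both, while still being reported to the sponsor. In a study of 3 to 5 patients any single death would be 20 to 33 percentage points of the result, so whether it appears matters. The documents do not show that misattribution is likely, and no probability is claimed.

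The conclusion assumes that a death judged unrelated is not automatically classed as leading to discontinuation, and that every enrolled patient is in the denominator. With fewer evaluable patients each death would weigh more.

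**What to change.** 1. In section 8, make death from any cause within 3 months of infusion, in all infused patients, the main safety indicator, or a co-main indicator beside transplant-related death.
2. Report death from any cause to the end of the 24-month follow-up as well.
3. In section 9, item (3), require every death to be listed individually with its date, cause and judged relatedness.
4. Give the count with its denominator, and state that with 3 to 5 patients the rate is very imprecise.

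The cost is wording only. Deaths are already reportable as serious adverse events and follow-up already runs to 24 months, so no visit, test or treatment rule changes. The downside for the sponsor is that the reported figure may be slightly less favourable.

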- 1) Blood routine: transplant 0d-1m at least 3 times a week; 1m-3m at least 1 time per week; 3m-6m at least 1 time per month; $\geq 6m$ at least once every 2 months. If the condition changes, the number of tests can be increased as appropriate.
- 2) DNA mosaicism rate of peripheral blood/bone marrow donors: +4, +7, +14, +30d, +90; 1 time per month for 1 year after transplantation; Within 3 years after transplantation. 1 time from March to June.
- 3) Thalassemia gene: 1 time before transplantation and 1 year after transplantation, once a month.
- 4) Liver and kidney function and serum ferritin: transplant 0d-1m at least once a week; 1m-3m at least 2 times a month; 3m-6m at least 1 time per month; $\geq 6m$ at least once every 2 months. If the condition changes, the number of tests can be increased as appropriate.
- 5) Cardiac color ultrasound: 1 time before transplantation, 1 time every 3 months within 1 year after transplantation.
- 6) Heart and liver MRI iron test: once before transplantation, once every 6 months within 1 year after transplantation.
- 7) Lymphocyte subsets: 1 time before transplantation, 1 time per month within 1 year after transplantation.
- 8) Cytokines: 1 time before transplantation, 1 time per month within 1 year after transplantation.
- 9) Thyroid function, ACTH and gonadal function: once before transplantation, once every 6 months within 1 year after transplantation.
- 10) Other items that need to be studied: thalassemia gene level, DNA chimerism status and child growth indicators.

6. Relevant provisions on concomitant medications, permitted drugs, cautionary drugs, prohibited drugs and concomitant treatment

Concomitant medications:

Permitted medications and concomitant treatments:

- (1) Other therapeutic drugs and treatments that the investigator believes do not have an

impact on the efficacy and safety evaluation of the research subjects are allowed.

(2) Any concomitant medication and concomitant therapy need to be approved by the investigator.

7. Research steps

One week before transplantation, the center evaluated the patients, and those who met the inclusion criteria were screened and enrolled. The study doctor will inform the benefits and risks of participating in this study in detail, and sign the informed consent form with full understanding of this study.

Transplantation protocol and procedure:

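### Section 9 applies chi-square tests at p<0.05, multivariate regression and a between-groups comparison to one uncontrolled arm of 3–5 patients

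*Protocol*

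**What the plan says.** Section 3(1), Research Design, describes the trial: "This study is a single-center, single-arm, prospective clinical study. There is no control and no blinding". Sections 2 and 5 give the planned size as 3–5 patients. Section 7 lists the transplantation plan as "Pretreatment: None". Section 8 names two main indicators, the donor cell engraftment rate and transplant-related death, both at 3 months. It gives no reference rate for either.

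Section 9 then sets these methods:

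- 9(1): "descriptive statistics and multivariate regression analysis were used", with counts for categorical data and medians for continuous data. It adds that "chi-square test and nonparametric test were mainly used" and takes p<0.05 as significant. It does not state whether tests are one- or two-sided.
- 9(4): descriptive statistics are used to "compare demographic characteristics and laboratory indicators at baseline between groups".
- 9(5): "The study endpoints could be analyzed according to the transplantation conditioning regimen, pre-transplantation remission status, age, neutrophil and platelet engraftment" time, and the "association between the primary and secondary study endpoints and different factors could be evaluated by COX regression". The wording here permits and does not require.

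**The concern.** Section 9 reads as a plan for a larger comparative study. This trial has no second group, so a between-groups baseline comparison has no object. No patient is conditioned, so conditioning regimen cannot be a subgroup factor. Neutrophil and platelet engraftment times are observed after infusion. They are outcomes, not baseline factors by which to explain engraftment or death.

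At this size the result of the named test depends on which version is run. An exact two-group test can never be significant, whatever the data show. Uncorrected chi-square can be significant without holding its 5% level. Section 2 aims to verify safety and efficacy, and a report could lean on such a p-value. The wide uncertainty around the two main indicators would meanwhile go unshown, because section 9 plans no interval for them.

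**Working it through.** **Inputs.** n = 3, 4 or 5 (sections 2 and 5); one arm, no control (section 3(1)); level 0.05 (section 9(1)). Two-sided testing is an assumption. The protocol gives no power, effect size or reference rate, so there is no figure of its own to reproduce. The check asks what the named methods can return at these sizes.

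**1. Two-group tests on a split of the single arm.** Split n patients into a and b. The most extreme table is perfect separation: all a have the outcome and none of the b do.

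- Fisher: each extreme table has probability 1/C(n,a). This is the two-sided p, except that the even 2 v 2 split has two equally extreme tables: 2/6 = 0.33.
- Uncorrected chi-square: the statistic equals n, on 1 degree of freedom.
- Worst-case type I error of uncorrected chi-square: at n=4 and n=5 only perfect separation gives p<0.05, so it is the maximum over the common rate p of p^a(1−p)^b + (1−p)^a p^b.

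| n | Split | Smallest Fisher p | Uncorrected chi-square p | Yates-corrected p | Worst-case type I error, uncorrected |
|---|---|---|---|---|---|
| 3 | 1 v 2 | 0.33 | 0.083 | 0.67 | 0 (cannot reach 0.05) |
| 4 | 1 v 3 | 0.25 | 0.0455 | 0.51 | 12.5% |
| 4 | 2 v 2 | 0.33 | 0.0455 | 0.32 | 12.5% |
| 5 | 1 v 4 | 0.20 | 0.025 | 0.40 | 8.3% |
| 5 | 2 v 3 | 0.10 | 0.025 | 0.19 | 6.25% |

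Example, 2 v 3: p²(1−p)³ + (1−p)²p³ = p²(1−p)², which is largest at p = 0.5, giving 1/16 = 6.25%. Example, 1 v 4: at p = 0.21, 0.21×0.79⁴ + 0.79×0.21⁴ = 0.083. The largest expected count in any cell of any 2×2 table at n=5 is 4×4/5 = 3.2, so every cell is below the usual minimum of 5.

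**2. Nonparametric tests.**

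- Smallest two-sided Mann-Whitney p, 2/C(n,a) at the most even split: 0.67, 0.33, 0.20 for n = 3, 4, 5.
- Smallest two-sided signed-rank p, 2/2ⁿ: 0.25, 0.125, 0.0625.
- Friedman over three visits, all patients ranking the visits alike, (1/6)^(n−1): 0.028, 0.0046, 0.0008.

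So rank-sum and before–after tests cannot reach 0.05, but a repeated-visit test can. Section 5 does collect suitable series, for example "Lymphocyte subsets: 1 time before transplantation, 1 time per month within 1 year after transplantation".

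**3. Regression.** An intercept plus two covariates uses 3 parameters, which leaves 0, 1 or 2 residual degrees of freedom at n = 3, 4, 5. Age and the two engraftment times from 9(5) make 4 parameters with an intercept: more than n at 3, equal to n at 4, one fewer at 5. In a Cox model, n−1 or more non-collinear covariates never give a finite estimate.

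**4. What the main indicators can show.** Exact Clopper-Pearson 95% limits for the best possible results:

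- No deaths, upper limit 1 − 0.025^(1/n): 71% (0/3), 60% (0/4), 52% (0/5).
- All engrafted, lower limit 0.025^(1/n): 29% (3/3), 40% (4/4), 48% (5/5).

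**The case against.** Section 9(1) names descriptive statistics first, with counts and medians, and 9(3) already asks for individual listing of serious adverse events from treatment and of events that lead to discontinuation. The Cox and subgroup analyses are only permitted. No stopping rule or success criterion depends on a p-value. The protocol does not say which endpoint chi-square is for, and a separate analysis plan may settle that.

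Most of this stands, and it limits the point. Four stronger readings are tempting, and the document does not support them:

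- *Regression is a main method.* The word mainly attaches to chi-square and nonparametric tests; regression is simply listed as used.
- *Nonparametric tests are useless here.* A Friedman test over three visits can reach 0.05 even at n=3. It does not, however, address 3-month engraftment or death.
- *The plan offers nothing for the main indicators.* Counts are already planned. What is lacking is an interval, and the tests emphasised in their place do not fit.
- *3–5 patients is itself the error.* A small pilot can be reasonable. The fault is in the analysis attached to it.

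In the copy at hand, heading 9(2), on the primary and secondary endpoints, has no text under it. The point does not rest on that, since an analysis plan could supply the detail. It rests on what 9(1), 9(4) and 9(5) do state.

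**Conclusion.** The point holds and should be fixed. Chi-square at p<0.05, multivariate regression, a between-groups comparison and a conditioning-regimen factor do not suit one uncontrolled, unconditioned arm of 3–5 patients. A two-group Fisher test cannot go below 0.10 at any planned size. Uncorrected chi-square can give 0.0455 or 0.025 at n = 4 or 5, but with a worst-case error of 12.5% or 6.25–8.3%, and applying the Yates correction reverses the verdict.

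The Fisher and chi-square minima follow from n alone once two-sided testing is assumed; Fisher stays at 0.10 or above one-sided too. The error rates are maxima over an unknown common rate and are lower elsewhere: for 2 v 3 at an assumed rate of 0.1, 0.1²×0.9² = 0.8%. They show that the 5% level is not guaranteed, not that it is exceeded at every rate. The regression result depends on how many covariates are entered, which 9(1) does not say.

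The consequence is misleading reporting. A reader might infer a fault in trial conduct or patient protection, but no decision in the protocol hangs on these tests.

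**What to change.** - **9(1):** keep the descriptive statistics. Delete chi-square, multivariate regression and the p<0.05 threshold. Add: *Results are listed per patient. Donor engraftment and transplant-related death at 3 months are reported as k/n of all patients who received the donor cell infusion, with exact Clopper-Pearson 95% confidence intervals; withdrawals are shown in the listing. Nonparametric tests are limited to exploratory exact within-patient tests of repeated laboratory measures (for example Friedman).* The infused-patient denominator is proposed because both indicators are timed from transplantation and the protocol allows withdrawal.
- **9(4):** describe the single cohort at baseline.
- **9(5):** delete the Cox and subgroup analyses. Show age and engraftment times in the per-patient listing.
- **Section 2:** describe the aim as a preliminary assessment of safety and efficacy, not as verifying them.

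The cost is wording only, with no new patients, visits or data. The downside is a more modest claim and fewer exploratory p-values.
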